12.1.4 Response Criteria

12.1.4.1 Evaluation of Target Lesions

Complete Response (CR): Disappearance of all target lesions. Any pathological lymph nodes (whether target or non-target) must have reduction in short axis to <10 mm (<1 cm).

Partial Response (PR): At least a 30% decrease in the sum of the diameters of target lesions, taking as reference the baseline sum diameters.

Progressive Disease (PD): At least a 20% increase in the sum of the diameters of target lesions, taking as reference the smallest sum on study (this includes the baseline sum if that is the smallest on study). In addition to the relative increase of 20%, the sum must also demonstrate an absolute increase of at least 5 mm (0.5 cm). (Note: the appearance of one or more new lesions is also considered progressions).

Stable Disease (SD): Neither sufficient shrinkage to qualify for PR nor sufficient increase to qualify for PD, taking as reference the smallest sum diameters while on study.

12.1.4.2 Evaluation of Non-Target Lesions

Complete Response (CR): Disappearance of all non-target lesions and normalization of tumor marker level. All lymph nodes must be non-pathological in size (<10 mm [<1 cm] short axis).

Note: If tumor markers are initially above the upper normal limit, they must normalize for a patient to be considered in complete clinical response.

Non-CR/Non-PD: Persistence of one or more non-target lesion(s) and/or maintenance of tumor marker level above the normal limits.

Progressive Disease (PD): Appearance of one or more new lesions and/or *unequivocal progression* of existing non-target lesions. *Unequivocal progression* should not normally trump target lesion status. It must be representative of overall disease status change, not a single lesion increase.

Although a clear progression of “non-target” lesions only is exceptional, the opinion of the treating physician should prevail in such circumstances, and the progression status should be confirmed at a later time by the review panel (or Principal Investigator).

12.1.4.3 Evaluation of Best Overall Response

The best overall response is the best response recorded from the start of the treatment until disease progression/recurrence (taking as reference for progressive disease the smallest measurements recorded since the treatment started). The patient's best response assignment will depend on the achievement of both measurement and confirmation criteria.

For Patients with Measurable Disease (i.e., Target Disease)

Target Lesions	Non-Target Lesions	New Lesions	Overall Response	Best Overall Response when Confirmation is Required*
CR	CR	No	CR	≥4 wks. Confirmation**
CR	Non-CR/Non-PD	No	PR	
CR	Not evaluated	No	PR	
PR	Non-CR/Non-PD/not evaluated	No	PR	≥4 wks. Confirmation**
SD	Non-CR/Non-PD/not evaluated	No	SD	Documented at least once ≥4 wks. from baseline**
PD	Any	Yes or No	PD	
Any	PD	Yes or No	PD	
Any	Any	Yes	PD	no prior SD, PR or CR

* See RECIST 1.1 manuscript for further details on what is evidence of a new lesion.
 ** Only for non-randomized trials with response as primary endpoint.

Note: Patients with a global deterioration of health status requiring discontinuation of treatment without objective evidence of disease progression at that time should be reported as “*symptomatic deterioration*.” Every effort should be made to document the objective progression even after discontinuation of treatment.

For Patients with Non-Measurable Disease (i.e., Non-Target Disease)

Non-Target Lesions	New Lesions	Overall Response
CR	No	CR
Non-CR/non-PD	No	Non-CR/non-PD*
Not all evaluated	No	not evaluated
Unequivocal PD	Yes or No	PD
Any	Yes	PD

* ‘Non-CR/non-PD’ is preferred over ‘stable disease’ for non-target disease since SD is increasingly used as an endpoint for assessment of efficacy in some trials so to assign this category when no lesions can be measured is not advised

12.1.5 Duration of Response

Duration of overall response: The duration of overall response is measured from the time measurement criteria are met for CR or PR (whichever is first recorded) until the first date that recurrent or progressive disease is objectively documented (taking as reference for progressive disease the smallest measurements recorded since the treatment started).

The duration of overall CR is measured from the time measurement criteria are first met for CR until the first date that progressive disease is objectively documented.

Duration of stable disease: Stable disease is measured from the start of the treatment until the criteria for progression are met, taking as reference the smallest measurements recorded since the treatment started, including the baseline measurements.

12.1.6 Progression-Free Survival

PFS is defined as the duration of time from registration to time of progressive disease as defined by RECIST 1.1 criteria or death from any cause, whichever occurs first.

13. STUDY OVERSIGHT AND DATA REPORTING / REGULATORY REQUIREMENTS

Adverse event lists, guidelines, and instructions for adverse event reporting can be found in Section 10 (Adverse Events: List and Reporting Requirements).

13.1 Study Oversight

This protocol is monitored at several levels, as described in this section. The Protocol Principal Investigator is responsible for monitoring the conduct and progress of the clinical trial, including the ongoing review of accrual, patient-specific clinical and laboratory data, and routine and serious adverse events; reporting of expedited adverse events; and accumulation of reported adverse events from other trials testing the same drug(s). The Protocol Principal Investigator and statistician have access to the data at all times through the CTMS web-based reporting portal.

For the Phase 1 portion of this study, all decisions regarding dose escalation/expansion/de-escalation require sign-off by the Protocol Principal Investigator through the CTMS/IWRS. In addition, for the Phase 1 portion, the Protocol Principal Investigator will have at least monthly, or more frequently, conference calls with the Study Investigators and the CTEP Medical Officer(s) to review accrual, progress, and adverse events and unanticipated problems.

All Study Investigators at participating sites who register/enroll patients on a given protocol are responsible for timely submission of data via Medidata Rave and timely reporting of adverse events for that particular study. This includes timely review of data collected on the electronic CRFs submitted via Medidata Rave.

All studies are also reviewed in accordance with the enrolling institution's data safety monitoring plan.

13.2 Data Reporting

Medidata Rave is a clinical data management system being used for data collection for this trial/study. Access to the trial in Rave is controlled through the CTEP-IAM system and role assignments.

Requirements to access Rave via iMedidata:

- A valid account, and
- Assigned a Rave role on the LPO or PO roster at the enrolling site of: Rave CRA, Rave Read Only, Rave CRA (LabAdmin), Rave SLA, or Rave Investigator.

Rave role requirements:

- Rave CRA or Rave CRA (Lab Admin) role, must have a minimum of an Associate Plus (AP) registration type,
- Rave Investigator role, must be registered as an Non-Physician Investigator (NPIVR) or Investigator (IVR), and
- Rave Read Only role, site staff must have at a minimum an Associates (A) registration type.
- Refer to <https://ctep.cancer.gov/investigatorResources/default.htm> for registration types and documentation required.

If the study has a DTL, individuals requiring write access to Rave must also be assigned the appropriate Rave tasks on the DTL.

Upon initial site registration approval for the study in Regulatory Support System (RSS), all persons with Rave roles assigned on the appropriate roster will be sent a study invitation e-mail from iMedidata. To accept the invitation, site staff must log in to the Select Login (<https://login.imedidata.com/selectlogin>) using their CTEP-IAM username and password, and click on the *accept* link in the upper right-corner of the iMedidata page. Site staff will not be able to access the study in Rave until all required Medidata and study specific trainings are completed. Trainings will be in the form of electronic learnings (eLearnings), and can be accessed by clicking on the link in the upper right pane of the iMedidata screen. If an eLearning is required and has not yet been taken, the link to the eLearning will appear under the study name in iMedidata instead of the *Rave EDC* link; once the successful completion of the eLearning has been recorded, access to the study in Rave will be granted, and a *Rave EDC* link will display under the study name.

Site staff that have not previously activated their iMedidata/Rave account at the time of initial site registration approval for the study in RSS will receive a separate invitation from iMedidata to activate their account. Account activation instructions are located on the CTSU website in the Data Management section under the Rave resource materials (Medidata Account Activation and Study Invitation Acceptance). Additional information on iMedidata/Rave is available on the CTSU members' website in the Data Management > Rave section at www.ctsu.org/RAVE/ or by contacting the CTSU Help Desk at [name] or by e-mail at [contact].

13.2.1 Method

This study will be monitored by the Clinical Trials Monitoring Service (CTMS). Data will be submitted to CTMS at least once every two weeks via Medidata Rave (or other modality if

approved by CTEP). Information on CTMS reporting is available at <http://www.theradex.com/clinicalTechnologies/?National-Cancer-Institute-NCI-11>. On-site audits will be conducted three times annually (one annual site visit and two data audits). For CTMS monitored studies, after users have activated their accounts, please contact the Theradex Help Desk at [contact] or by email at [contact] for additional support with Rave and completion of CRFs.

13.2.2 Responsibility for Data Submission

For ETCTN trials, it is the responsibility of the PI(s) at the site to ensure that all investigators at the ETCTN Sites understand the procedures for data submission for each ETCTN protocol and that protocol specified data are submitted accurately and in a timely manner to the CTMS via the electronic data capture system, Medidata Rave.

Data are to be submitted via Medidata Rave to CTMS on a real-time basis, but no less than once every 2 weeks. The timeliness of data submissions and timeliness in resolving data queries will be tracked by CTMS. Metrics for timeliness will be followed and assessed on a quarterly basis. For the purpose of Institutional Performance Monitoring, data will be considered delinquent if it is greater than 4 weeks past due.

Data from Medidata Rave and CTEP-AERS is reviewed by the CTMS on an ongoing basis as data is received. Queries will be issued by CTMS directly within Rave. The queries will appear on the Task Summary Tab within Rave for the CRA at the ETCTN to resolve. Monthly web-based reports are posted for review by the Drug Monitors in the IDB, CTEP. Onsite audits will be conducted by the CTMS to ensure compliance with regulatory requirements, GCP, and NCI policies and procedures with the overarching goal of ensuring the integrity of data generated from NCI-sponsored clinical trials, as described in the ETCTN Program Guidelines, which may be found on the CTEP

(http://ctep.cancer.gov/protocolDevelopment/electronic_applications/adverse_events.htm) and CTSU websites.

CTMS will utilize a core set of eCRFs that are Cancer Data Standards Registry and Repository (caDSR) compliant (<http://cbiit.nci.nih.gov/ncip/biomedical-informatics-resources/interoperability-and-semantics/metadata-and-models>). Customized eCRFs will be included when appropriate to meet unique study requirements. The PI is encouraged to review the eCRFs, working closely with CTMS to ensure prospectively that all required items are appropriately captured in the eCRFs prior to study activation. CTMS will prepare the eCRFs with built-in edit checks to the extent possible to promote data integrity.

CDUS data submissions for ETCTN trials activated after March 1, 2014, will be carried out by the CTMS contractor, Theradex. CDUS submissions are performed by Theradex on a monthly basis. The trial's lead institution is responsible for timely submission to CTMS via Rave, as above.

Further information on data submission procedures can be found in the ETCTN Program Guidelines

(http://ctep.cancer.gov/protocolDevelopment/electronic_applications/adverse_events.htm).

13.3 Data Quality Portal

The Data Quality Portal (DQP) provides a central location for site staff to manage unanswered queries and form delinquencies, monitor data quality and timeliness, generate reports, and review metrics.

The DQP is located on the CTSU members' website under Data Management. The Rave Home section displays a table providing summary counts of Total Delinquencies and Total Queries. DQP Queries, DQP Delinquent Forms, and the DQP Reports modules are available to access details and reports of unanswered queries, delinquent forms, and timeliness reports. Review the DQP modules on a regular basis to manage specified queries and delinquent forms.

The DQP is accessible by site staff that are rostered to a site and have access to the CTSU website. Staff that have Rave study access can access the Rave study data using a direct link on the DQP.

To learn more about DQP use and access, click on the Help icon displayed on the Rave Home, DQP Queries, and DQP Delinquent Forms modules.

Note: Some Rave protocols may not have delinquent form details or reports specified on the DQP. A protocol must have the Calendar functionality implemented in Rave by the Lead Protocol Organization (LPO) for delinquent form details and reports to be available on the DQP. Site staff should contact the LPO Data Manager for their protocol regarding questions about Rave Calendaring functionality.

13.4 CTEP Multicenter Guidelines

N/A

13.5 Collaborative Agreements Language

The agent(s) supplied by CTEP, DCTD, NCI used in this protocol is/are provided to the NCI under a Collaborative Agreement (CRADA, CTA, CSA) between the Pharmaceutical Company(ies) (hereinafter referred to as "Collaborator(s)") and the NCI Division of Cancer Treatment and Diagnosis. Therefore, the following obligations/guidelines, in addition to the provisions in the "Intellectual Property Option to Collaborator" (http://ctep.cancer.gov/industryCollaborations2/intellectual_property.htm) contained within the terms of award, apply to the use of the Agent(s) in this study:

1. Agent(s) may not be used for any purpose outside the scope of this protocol, nor can Agent(s) be transferred or licensed to any party not participating in the clinical study. Collaborator(s) data for Agent(s) are confidential and proprietary to Collaborator(s) and shall be maintained as such by the investigators. The protocol documents for studies utilizing Agents contain confidential information and should not be shared or distributed without the permission of the

NCI. If a copy of this protocol is requested by a patient or patient's family member participating on the study, the individual should sign a confidentiality agreement. A suitable model agreement can be downloaded from: <http://ctep.cancer.gov>.

2. For a clinical protocol where there is an investigational Agent used in combination with (an)other Agent(s), each the subject of different Collaborative Agreements, the access to and use of data by each Collaborator shall be as follows (data pertaining to such combination use shall hereinafter be referred to as "Multi-Party Data"):
 - a. NCI will provide all Collaborators with prior written notice regarding the existence and nature of any agreements governing their collaboration with NCI, the design of the proposed combination protocol, and the existence of any obligations that would tend to restrict NCI's participation in the proposed combination protocol.
 - b. Each Collaborator shall agree to permit use of the Multi-Party Data from the clinical trial by any other Collaborator solely to the extent necessary to allow said other Collaborator to develop, obtain regulatory approval or commercialize its own Agent.
 - c. Any Collaborator having the right to use the Multi-Party Data from these trials must agree in writing prior to the commencement of the trials that it will use the Multi-Party Data solely for development, regulatory approval, and commercialization of its own Agent.
3. Clinical Trial Data and Results and Raw Data developed under a Collaborative Agreement will be made available to Collaborator(s), the NCI, and the FDA, as appropriate and unless additional disclosure is required by law or court order as described in the IP Option to Collaborator (http://ctep.cancer.gov/industryCollaborations2/intellectual_property.htm). Additionally, all Clinical Data and Results and Raw Data will be collected, used and disclosed consistent with all applicable federal statutes and regulations for the protection of human subjects, including, if applicable, the *Standards for Privacy of Individually Identifiable Health Information* set forth in 45 C.F.R. Part 164.
4. When a Collaborator wishes to initiate a data request, the request should first be sent to the NCI, who will then notify the appropriate investigators (Group Chair for Cooperative Group studies, or PI for other studies) of Collaborator's wish to contact them.
5. Any data provided to Collaborator(s) for Phase 3 studies must be in accordance with the guidelines and policies of the responsible Data Monitoring Committee (DMC), if there is a DMC for this clinical trial.
6. Any manuscripts reporting the results of this clinical trial must be provided to CTEP by the Group office for Cooperative Group studies or by the principal investigator for non-Cooperative Group studies for immediate delivery to Collaborator(s) for advisory review and comment prior to submission for publication. Collaborator(s) will have 30 days from the date of receipt for review. Collaborator shall have the right to request that publication be delayed for up to an additional 30 days in order to ensure that Collaborator's confidential and proprietary data, in addition to Collaborator(s)'s intellectual property rights, are protected.

Copies of abstracts must be provided to CTEP for forwarding to Collaborator(s) for courtesy review as soon as possible and preferably at least three (3) days prior to submission, but in any case, prior to presentation at the meeting or publication in the proceedings. Press releases and other media presentations must also be forwarded to CTEP prior to release. Copies of any manuscript, abstract and/or press release/ media presentation should be sent to:

Email: [contact]

The Regulatory Affairs Branch will then distribute them to Collaborator(s). No publication, manuscript or other form of public disclosure shall contain any of Collaborator's confidential/proprietary information.

APPENDIX A PERFORMANCE STATUS CRITERIA

ECOG Performance Status Scale		Karnofsky Performance Scale	
Grade	Descriptions	Percent	Description
0	Normal activity. Fully active, able to carry on all pre-disease performance without restriction.	100	Normal, no complaints, no evidence of disease.
		90	Able to carry on normal activity; minor signs or symptoms of disease.
1	Symptoms, but ambulatory. Restricted in physically strenuous activity, but ambulatory and able to carry out work of a light or sedentary nature (e.g., light housework, office work).	80	Normal activity with effort; some signs or symptoms of disease.
		70	Cares for self, unable to carry on normal activity or to do active work.
2	In bed <50% of the time. Ambulatory and capable of all self-care, but unable to carry out any work activities. Up and about more than 50% of waking hours.	60	Requires occasional assistance, but is able to care for most of his/her needs.
		50	Requires considerable assistance and frequent medical care.
3	In bed >50% of the time. Capable of only limited self-care, confined to bed or chair more than 50% of waking hours.	40	Disabled, requires special care and assistance.
		30	Severely disabled, hospitalization indicated. Death not imminent.
4	100% bedridden. Completely disabled. Cannot carry on any self-care. Totally confined to bed or chair.	20	Very sick, hospitalization indicated. Death not imminent.
		10	Moribund, fatal processes progressing rapidly.
5	Dead.	0	Dead.

APPENDIX B FORMULA TO ESTIMATE RENAL FUNCTION USING SERUM CREATININE

Formula to estimate renal function using serum creatinine provided by the NCI's Investigational Drug Steering Committee (IDSC) Pharmacological Task Force in table below.

1. Estimated creatinine clearance (ClCr) by the Cockcroft-Gault (C-G) equation (Cockcroft and Gault, 1976).

[figure not shown]
$$CLcr \text{ (mL/min)} = \frac{[140 - \text{age (years)}] \times \text{weight (kg)}}{72 \times \text{serum creatinine (mg / dL)}} \{ \times 0.85 \text{ for female patients} \}$$

Followed by conversion to a value normalized to 1.73 m² with the patient's body surface area (BSA).

References

1. Cockcroft, D.W. and M.H. Gault. (1976). Prediction of creatinine clearance from serum creatinine. *Nephron*. 16:31-41.

APPENDIX C PATIENT CLINICAL TRIAL WALLET CARD

APPENDIX D PATIENT'S MEDICATION DIARY – ONCE DAILY (QD)

CTEP-assigned Protocol # 10388

Local Protocol # _____

PATIENT'S MEDICATION DIARY

Today's date _____ Agent _____ Triapine _____
Patient Name _____ (initials acceptable) Patient Study ID _____

INSTRUCTIONS TO THE PATIENT:

1. Complete one form for each cycle. Each cycle is 8 weeks.
2. You will take your dose of triapine every day for the first 14 days of the cycle. You will take _____ 50 mg capsules every day for the first 14 days of the cycle. You need to fast (except for water) for 2 hours prior to dosing and for 1 hour after ingesting the oral dose. You should swallow the capsule whole. **Do not open the capsules or take capsules until the bottle is empty.**
3. Record the date, the number of capsules you took, and when you took them.
4. If you have any comments or notice any side effects, please record them in the Comments column.
5. Please return the forms to your physician when you go for your next appointment.

Day	Date	What time was dose taken?	# of capsules taken	Comments
1				
2				
3				
4				
5				
6				
7				
8				
9				
10				
11				
12				
13				
14				

Do not take triapine after Day 14 of each cycle

Physician's Office will complete this section:

1. Date patient started protocol treatment _____
2. Date patient was removed from study _____
3. Patient's planned total daily dose _____
4. Total number of pills taken this month (each size) _____
5. Physician/Nurse/Data Manager's Signature and Date _____

Patient's
signature: _____

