6. TREATMENT PLAN

6.1 Agent Administration in Dose Escalation Phase

Treatment will be administered on an outpatient or inpatient basis per institutional standard operating procedures (SOPs). Reported adverse events and potential risks are described in Section 10. Appropriate dose modifications are described in Section 7. No investigational or commercial agents or therapies other than those described below may be administered with the intent to treat the patient's malignancy.

Oral triapine will be given at the assigned phase 1 dose level. Patients will be asked to fast (except for water) for 2 hours prior to dosing and for 1 hour after ingesting the oral dose (triapine complexes strongly with iron ions). Patients will ingest one dose of triapine within 90 minutes after Lutetium Lu 177 Dotatate treatment and once daily after that for 14 days. Ninety-nine percent of Lutetium Lu 177 Dotatate radiation is undetectable by Day 14. Lutetium Lu 177 Dotatate will be administered as IV infusion per FDA label every 2 months at dose of 200 mCi for total of 4 doses. All dose cohorts will be treated with same dose of Lutetium Lu 177 Dotatate.

Dose Escalation Schedule		
Dose Level	Dose *	
	Triapine	Lutetium Lu 177 Dotataate
Level -2	50 mg PO QOD, Days 1-14	200 mCi IV, Day 1
Level -1	50 mg PO QD, Days 1-14	
Level 1 [#]	100 mg PO QD, Days 1-14	
Level 2	150 mg PO QD, Days 1-14	
Level 3	200 mg PO QD, Days 1-14	

* Doses are stated as exact dose in units (e.g., mg/m², mcg/kg, etc.) rather than as a percentage.
[#] Starting dose.

Regimen Description					
Agent	Premedications; Precautions	Dose	Route	Schedule	Cycle Length
Triapine	Fast (except for water) for 2 hours prior to dosing and for 1 hour after ingesting the oral dose	As per assigned dose level (See dose escalation schedule above)	Oral;	Days 1-14 of each cycle; on Day 1, within 90 minutes after Lutetium Lu 177 Dotataate treatment.	8 weeks (56 days)
Lutetium Lu 177 Dotataate	Administer antiemetics 30 minutes before the recommended amino acid solution. Administer amino acid solution IV 30 minutes before Lutetium Lu 177 Dotataate.	200 mCi	IV; Please refer to section 8.2.1 for details regarding Lutetium Lu 177 Dotataate route of administration.	Day 1 of each cycle	

The patient will be requested to maintain a medication diary of each dose of triapine (Appendix D). The medication diary will be returned to clinic staff at the end of each course.

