7.2 Recommended Dose Modifications of Triapine

Dose modification should follow the triapine dose levels in the dose escalation table in Section 6.1.

Nausea/vomiting	Management/Next Dose for Triapine
≤ Grade 2	No change in dose. Treat with antiemetics.
Grade 3	Hold ^a until ≤ Grade 2. Resume at one dose level lower, if indicated. Treat with antiemetics.
Grade 4	Off protocol therapy ^c

^aPatients should hold triapine if N/V refractory to anti-emetic therapy.

^bIf appropriate antiemetic treatment does not resolve toxicity down to grade 2 or less within 72 hours.

^cOff protocol therapy and continue standard of care treatment per treating physician.

Diarrhea	Management/Next Dose for Triapine
≤ Grade 2	No change in dose. Treat with antidiarrheal therapy.
Grade 3	Treat with antidiarrheal therapy. Hold ^a until ≤ Grade 2. Resume at one dose level lower, if indicated ^b
Grade 4	Off protocol therapy ^b

^aPatients should hold triapine if diarrhea refractory to anti-diarrheal (Loperamide is recommended). Adjunct anti-diarrheal therapy is permitted and should be recorded when used.
^bOff protocol therapy and continue standard of care treatment per treating physician.

Neutropenia	Management/Next Dose for Triapine
≤ Grade 2	No change in dose
Grade 3	No change in dose
Grade 4	Off protocol therapy ^a

^aOff protocol therapy and continue standard of care treatment per treating physician.

Thrombocytopenia	Management/Next Dose for Triapine
≤ Grade 1	No change in dose
Grade 2	No change in dose
Grade 3	No change in dose
Grade 4	Off protocol therapy ^a

^aOff protocol therapy and continue standard of care treatment per treating physician.

Non-hematologic toxicity	Management/Next Dose for Triapine
≤ Grade 1	No change in dose
Grade 2	Hold ^{a, b} until ≤ Grade 1 (See NOTE below)
Grade 3	Hold ^c until < Grade 1 (See NOTE below)
Grade 4	Off protocol therapy ^b

^aPatients requiring a delay of >2 weeks should go off protocol therapy.
^b Grade 2 hypertension unrelated to study drugs in a patient with history of chronic hypertension does not warrant holding treatment.
^cOff protocol therapy and continue standard of care treatment per treating physician.
 NOTE: Decision to maintain dose or resume at dose reduction must be reviewed with study PI.

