8.1 CTEP IND Agent - Triapine

8.1.1 Triapine (NSC # 663249)

Chemical Name: 3-aminopyridine-2-carboxaldehyde thiosemicarbazone

Other Names: 3-AP

Classification: Triapine, an α -heterocyclic carboxaldehyde thiosemicarbazone (HCT), is a ribonucleotide reductase (RNR) inhibitor that acts on the M2 (R2) subunit. The HCTs are the most potent RNR inhibitors, being 65 -5,000 times more potent than hydroxyurea.

Mechanism of Action: Ribonucleotide reductase (RNR) inhibitor

CAS Registry Number: 143621-35-6

Molecular Formula: C₇H₉N₅S **M.W.:** 195

Approximate Solubility: Water = 0.1 mg/mL
Ethanol = 1.25 mg/mL
PEG-300 = 15 mg/mL

How Supplied: Triapine Capsules are supplied by Nanopharmaceutics, LLC and distributed by the CTEP, DCTD, NCI. Each triapine Capsule contains 50 mg of triapine in combination with Starch 1500 and Magnesium Stearate in a size 1, hard gelatin, white, opaque capsule. Each bottle contains 30 capsules.

Storage: Store triapine Capsules at room temperature 25°C, excursions permitted to 15°C to 30°C.

If a storage temperature excursion is identified, promptly return triapine Capsules to between 15 and 30°C and quarantine the supplies. Provide a detailed report of the excursion (including documentation of temperature monitoring and duration of the excursion) to [contact] for determination of suitability.

Stability: Shelf-life stability studies of triapine Capsules are on-going.

Route of Administration: Oral administration. Patients will be asked to fast (except for water) for 2 hours prior to dosing and for 1 hour after ingesting the oral dose. Capsules should not be opened.

Availability

Triapine is an investigational agent supplied to investigators by the Division of Cancer Treatment and Diagnosis (DCTD), NCI.

If the study agent is provided by the NCI under a Collaborative Agreement with the agent manufacturer, the text below must be included in the protocol. Information on the study agent's Collaborative Agreement status will be provided in the approved LOI response letter.

Triapine is provided to the NCI under a Collaborative Agreement between the Pharmaceutical Collaborator and the DCTD, NCI (see Section 13.5).

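### The only triapine diary (Appendix D) is a once-daily form, so a patient reduced to Level -2 who follows it takes 14 doses per cycle instead of 7

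*Combined protocol and SAP*

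**What the plan says.** The dose table in Section 6.1 (repeated in the Schema) has five triapine levels. Levels -1, 1, 2 and 3 are taken daily on Days 1-14. Level -2 is "50 mg PO QOD, Days 1-14", and the Schema footnote defines QOD as every other day. Section 6.1 opens its dosing paragraph with "Oral triapine will be given at the assigned phase 1 dose level", but a later sentence in that paragraph describes the doses after the first as once daily.

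Level -2 is also open as a reduction step. Section 7.2 says "Dose modification should follow the triapine dose levels in the dose escalation table in Section 6.1". For Grade 3 nausea or vomiting and for Grade 3 diarrhea it says "Resume at one dose level lower, if indicated".

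Sections 6.1 and 6.3.2 both name Appendix D as the patient's diary, and the table of contents lists no other. Its title marks it as once daily. Its instructions say "You will take your dose of triapine every day for the first 14 days of the cycle" and then give a blank followed by "50 mg capsules every day for the first 14 days of the cycle". Below these are 14 numbered daily rows. The section for the physician's office asks for the "planned total daily dose" and has no item for frequency. On supply, Section 8.1.1 says "Each triapine Capsule contains 50 mg of triapine".

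**The concern.** Levels -1, 1, 2 and 3 differ in the number of capsules per day, which the diary's blank can record. Level -2 differs from Level -1 only in how often the capsule is taken, and the form fixes that in print. A diary correctly completed for Level -2 therefore reads the same as one for Level -1.

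The form instructs the patient as well as recording doses. Someone stepped down from Level -1 to Level -2 for toxicity, and following the diary, would get no reduction in that cycle. The returned diary and the office pill count would reveal this only afterwards.

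**Working it through.** The protocol states no dose count for Level -2, so there is no figure to reproduce. The check is a count of dosing days.

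**Inputs**
- Capsule strength: 50 mg (Section 8.1.1).
- Dose and frequency at each level: dose table, Section 6.1.
- Meaning of QOD: every other day (Schema).
- Diary frequency: daily, 14 rows (Appendix D).

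**Dosing days within Days 1-14**
- Daily: 14.
- Every other day: Days 1, 3, 5, 7, 9, 11 and 13, which is 7. Starting on Day 2 also gives 7.

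**Formula:** capsules per cycle = (mg per dose ÷ 50) × dosing days; mg per cycle = capsules × 50.

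| Regimen | Capsules per dose | Dosing days | Capsules per cycle | mg per cycle |
|---|---|---|---|---|
| Level 2 (RP2D, 150 mg daily) | 3 | 14 | 42 | 2,100 |
| Level 1 (100 mg daily) | 2 | 14 | 28 | 1,400 |
| Level -1 (50 mg daily) | 1 | 14 | 14 | 700 |
| Level -2 as assigned | 1 | 7 | 7 | 350 |
| Level -2 by Appendix D | 1 | 14 | 14 | 700 |

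**Comparison**
- Diary against assignment at Level -2: 700 / 350 = 2.0, an excess of 700 − 350 = 350 mg in a full affected cycle.
- The diary total equals Level -1 exactly, so the step from -1 to -2 disappears.
- Against the RP2D: 700 / 2,100 = 0.33. Each single dose is still 50 mg, and the reductions made before Level -2 remain in force.

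**Reach**
- One-level steps down to Level -2: two from Level 1, three from Level 2, four from Level 3.
- Section 6.3 reports escalation patients at 100, 150 and 200 mg only, and the expansion cohort starts at 150 mg.
- Section 7.2 has no triapine step-down for neutropenia or thrombocytopenia.
- No patient is described at Level -2, and Section 2.5.2.1 records that accrual has closed.

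**The case against.** The mismatch and the count are not in dispute. The case against is that they hardly matter.

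- **Investigator review.** The explicit one-level step-down is written only for Grade 3 nausea or vomiting and Grade 3 diarrhea. For other non-hematologic toxicity, Section 7.2 requires the decision to be reviewed with the study PI. After methemoglobin-related hypoxia, Section 7.2.1 leaves a lower dose to the Principal Investigator. Grade 4 events in the 7.2 tables end protocol therapy.
- **Few cycles.** Treatment is at most four cycles. Assuming one reduction per cycle, a patient starting at Level 2 reaches Level -2 only in Cycle 4, a Level 1 starter in Cycle 3, and a Level 3 starter not at all.
- **Timing.** Section 5.5.3.4 dates the biobanking decision, taken after accrual closed, to 12/13/2022. Suppose the last patient registered that day and began treatment at the 30-day limit in Section 4.4, about 12 January 2023. Without delays, that patient would be at Cycle 3 Day 14 on the version date of 17 May 2023, with one triapine course left.
- **Site staff.** Section 6.1.1 has patients instructed to take the assigned level, and the opening of 6.1, the regimen table and study calendar note A say the same. Staff could annotate the diary, strike out rows or correct it verbally.

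All of this stands as a limit on reach. The cycle-by-cycle limit assumes one reduction per cycle, which the protocol does not state, and treatment delays would move the dates. Staff correction is plausible, and for staff the dose table would ordinarily govern. However, the protocol neither provides an every-other-day form nor tells sites to alter this one, and the form has no frequency field. None of these points makes the printed instruction right for Level -2.

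**Conclusion.** The concern holds, at the lowest level of importance. Appendix D gives the wrong dosing frequency for a level the protocol permits: 14 doses (700 mg) per cycle instead of 7 (350 mg), which cancels the final toxicity reduction for that cycle. The once-daily wording in Section 6.1 is a secondary conflict, because the same paragraph defers to the assigned level and the dose table follows directly.

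The harm assumes that a patient reaches Level -2, receives the diary as printed without other instruction, and follows it. No such patient is described, and few if any could still arise. The point concerns patient instructions and dosing safety; no endpoint, estimate or design property changes.

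**What to change.** In Appendix D, replace both printed statements of daily dosing with a frequency that site staff fill in. Alternatively, add a second diary for Level -2 with rows for Days 1, 3, 5, 7, 9, 11 and 13 only. In Section 6.1, amend the sentence on doses after the first so that it reads once daily, or every other day at Level -2.

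The cost is two wording edits, or one edit and one extra form page. Design, visits, data collection and analysis are unchanged. With accrual closed, the main practical benefit may be to keep the error out of any later protocol that reuses this dose table and diary.
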